Delay discounting task	X	X	X	X	X	X			
N back test	X	X	X	X	X	X			
Stroop Test	X	X	X	X	X	X			
Young Mania Rating Scale	X	X	X	X	X	X			
DKEFS Verbal Fluency Test	X	X	X	X	X	X			
Pressure pain threshold	X	X	X	X	X	X			
Sham validating measure				X					
Trail making A and B	X	X	X	X	X	X			
Visual Analog Scales**	X	X	X	X	X	X			
MINI International	X								
Neuropsychiatric Interview (MINI)									
Randomization	X								

^{**} This assessment will be collected 3 times per day pre and post rTMS.

Safety Assessments

Research staff will use the MedDRA System Organ Class (SOC) and preferred term (PT) to document adverse events, which will be assessed at each treatment, and at follow-up visits.

This protocol will not modify patient care and our visits will not interfere with regular clinical care, except in the case of imminent danger to the patient or others in which appropriate measures will be taken, like contacting the primary treatment team and placing the patient on 1:1 observation until evaluation by the primary team.

STUDY POPULATION

Participant recruitment will occur at the inpatient units at the Psychiatric Research Institute (PRI). Target sample size is 20, which will be randomized into active or sham groups (1:1). Considering 40% attrition rate we plan to recruit 28 participants.

Recruitment: Recruitment will be facilitated by the PI's role of PRI inpatient attending physician. The success of this proposal depends heavily on the ability to recruit patients very soon after hospitalization for

PI: [name]

suicide ideation or behavior.

All participants will be compensated \$40 for their participation in each of the 3 rTMS sessions of the active phase of the study and the 2 follow-up sessions. Participants can earn a total of \$200 for completing the entire study, including both follow up visits.

Inclusion Criteria

- a) Age 18-60 years, of all races and ethnicities;
- b) Admitted voluntarily to the adult psychiatric inpatient at PRI;
- c) Suffering from a current depressive episode as defined by the DSM-V
- d) Currently have diagnoses of major depressive disorder
- e) Reason for hospitalization should be a recent suicide attempt or suicidal ideation
- f) Current severe suicidal ideation defined by a score >7 in the Beck Scale for Suicidal Ideation
- g) Must pass the TMS safety checklist (TASS)
- h) Women of childbearing age must have a negative result on a pregnancy test
- i) Ability to read, write and speak English.

Exclusion Criteria

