3. Effects on Mood: Dysphoria with crying has been induced after left prefrontal stimulation (33). In contrast, high-frequency stimulation of the right prefrontal cortex may transiently improve mood as rapid-rate rTMS has been shown to be a safe and effective treatment in subjects with depression.

Since this study aims to assess the effect of rTMS on suicidal ideation, all subjects will be experiencing suicidality by definition. Hence, subjects will already be under ongoing intensive psychiatric inpatient care with suicide precautions. To assess worsening of suicidal ideation we will perform daily assessments and share with the treatment team in case of worsening of suicidal ideation.

There is a risk of worsening depression as a result of rTMS treatment. The subjects are inpatient and will be assessed daily by the treatment team and followed up 3 and 6 months after treatment. If worsening depression occurs during the study, the treatment will be stopped and the subject will be withdrawn from the study.

There is a risk of mania/hypomania in subjects with or without bipolar disorder. Also the use of rTMS may increase the risk of suicide or suicidal ideation. Subjects will be assessed daily for the development of mania or hypomania with the Young Mania Rating Scale. If mania/hypomania develops during the study, the subject will be withdrawn from the study and the treatment team will be informed in order to initiate adequate treatment. This would represent a relatively minor adjustment since all subjects will already be inpatient in the psychiatric ward.

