- 2. The study physician or nurse will monitor the subject during and after rTMS for twitching of a hand muscle, such as the abductor pollicis brevis or the first dorsal interosseous muscle, on the side contralateral to the rTMS treatment site as this is the most sensitive procedure for detecting after discharges, muscle contraction persisting after stimulation. Subjects will also be monitored by inspection of other body parts that might be affected (e.g., the left arm after right frontal stimulation) or for symptoms that might occur (visual disturbance after occipitotemporal stimulation); should these be observed, the session will be terminated, and the subject will not be tested again using those stimulation parameters.
- 3. All subjects will wear ear plugs during testing sessions.
- 4. The study physician or nurse will be present when a subject is receiving TMS.
- 5. The PI, study physician, or nurse will stock and maintain the laboratory with the emergency supplies described below.
- 6. If a subject were to have a seizure during or immediately following the study, the study physician or nurse would attend to the subject and administer standard precautionary procedures for seizures. The following precautions will be performed:
 - Providing clear access to the subject.
 - Immediately terminate pulsing.
 - Rapidly remove the coil from the subject.
 - Place the patient in as close as possible a horizontal position on the floor onto a floor mat turning patient gently onto one side. This will help the patient to breathe.
 - Check patency of patient airway, verify adequate airflow.
 - Place a soft flat pillow under patient head (to help prevent injury).
 - Check circulation (peripheral pulses).
 - Time duration of the seizure. Most seizures last ≤ 2 minutes.
 - The PI will be notified

Knowing that all TMS-induced seizures to date have spontaneously resolved without interventions, the following will be done only if the seizure or event persists past 5 minutes:

- Ativan 2 mg will be given IM.
- The PI will notify primary clinical team for the PRI inpatient unit of the seizure occurrence.
- The patient will be transported back to inpatient unit via stretcher to be placed under constant observation.
- 7. Prior to participation, subjects will be fully informed of the possibility of seizure, the plan for care in event of a seizure, and any foreseeable financial or medical consequences resulting from a seizure.

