- 8. Pregnancy tests results from medical records will be obtained for women who are of childbearing age and for whom a possibility of pregnancy is indicated.

PI: [name]

Protection Against Risks Associated with Loss of Confidentiality

All data will be safe-guarded in accordance with HIPAA. The investigators use codes to keep subject information secure. Data encryption software is required at UAMS for computers with confidential information. All study staff will have current documentation of HIPAA and CITI training.

Protection Against Risks Associated with Interviews and Questionnaires

Subjects may decline to answer any questions that may make subjects uncomfortable, including questions that may be asked of subjects by the study physician. Subjects may be excluded if the information is necessary to prevent adverse events associated with study procedures.

Protection Against Risks Associated with Blood Draw

Blood draws will be performed by trained staff in an appropriate setting to minimize adverse risks.

Potential Benefits

Suicidal ideation and behavior are very distressing and we anticipate that subjects will be eager to participate in this study with the hope of reducing suicidal ideation. This study will allow us to gather important data with regard to the anticipated efficacy of rTMS for the alleviation of suicidal ideation, thus being of benefit to all subjects who suffer from suicidal ideation.

SAFETY ASSESSMENTS

Safety monitoring will include the following: 1) the PI is the designated responsible entity; 2) subjects will be videotaped during rTMS in order to have a visual record of seizure activity if it occurs (we turn on a WebCam during each rTMS session and discard data if no adverse event occurs); 3) during and immediately following stimulation, subjects will be inspected for signs of twitching and movement indicative of seizure by the study physician or nurse; 4) in the event of seizure, the plan outlined under protection against risk will be followed by study personnel; 5) the PI will report any adverse events to the IRB and funding agency Any seizure resulting from this study would immediately be published so as to add to the collective body of information on TMS. The PI will prepare regularly scheduled reports to the IRB, as required, in a timely fashion.

Subjects will be withdrawn from the study if:

- they experience a seizure or a reaction to rTMS that looks like a seizure
- experience severe pain, like dental pain

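### The seizure plan requires telling the inpatient team, and constant observation, only when a seizure passes 5 minutes, although the protocol expects most to end within 2

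*Combined protocol and SAP*

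**What the plan says.** The seizure plan is item 6 of Protection Against Risks Associated with TMS, and it has two lists.

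The first applies to every seizure. Staff stop stimulation, take the coil away, position and protect the patient, check airway and circulation, time the event and notify the PI. Its timing step notes: "Most seizures last ≤ 2 minutes".

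The second list opens with a reason, "Knowing that all TMS-induced seizures to date have spontaneously resolved without interventions", and a condition: its steps are carried out "only if the seizure or event persists past 5 minutes". There are three steps:

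- Ativan 2 mg intramuscularly.
- Word from the PI to the ward's primary clinical team that a seizure has happened.
- "The patient will be transported back to inpatient unit via stretcher to be placed under constant observation".

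The Safety Assessments section makes this the operative plan: "in the event of seizure, the plan outlined under protection against risk will be followed by study personnel". The Data and Safety Monitoring Plan repeats that instruction. Neither section adds a separate route for shorter seizures.

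**The concern.** A 5-minute limit is a natural place to put a drug. It is an odd place to put a telephone call to the treating team or an order for observation. The wording is an explicit, exclusive condition, so staff who follow it exactly have no instruction to tell the ward about a seizure that stops after a minute or two. The list for every seizure ends with notice to the PI. It has no hand-over to the unit and no step for getting the patient back there.

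The protocol calls seizure the most serious known risk of TMS (Risks Associated with TMS, item 1). It also says that its 5-second trains exceed the 4.2 seconds the FDA regards as the safe maximum at these settings, which increases the listed risks (item 12). The subjects are acutely suicidal inpatients whose ordinary care, prescribing included, stays with the ward team. What is at stake is whether that team knows that a seizure has happened.

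**Working it through.** The plan gives no figure to reproduce. The check compares the trigger with the protocol's own expectation, tests the stated reason against each conditional step, and looks for another rule that would fill the gap.

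**1. Trigger against expected duration.** Both inputs come from item 6: a trigger of more than 5 minutes, and 2 minutes or less for most seizures. The ratio is 5 / 2 = 2.5. On the protocol's own statement, most seizures end well before the second list starts. The exact share cannot be computed, because the documents give no distribution of durations beyond that statement.

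**2. The reason against each step.**

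| Step under the 5-minute condition | Does spontaneous resolution justify waiting? |
|---|---|
| Ativan | Yes. A drug is not needed if the seizure stops unaided. |
| Notice to the primary clinical team | No. The team needs to know whether or not the seizure stopped unaided. |
| Return to the unit under constant observation | No. Observation concerns the period after the seizure, however it ended. |

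One of the three steps fits the reason given.

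**3. Other rules that might cover a short seizure.**

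- *Withdrawal (Safety Assessments).* Any seizure, or a reaction resembling one, removes the subject from the study. This does not call for notice to the ward.
- *Adverse event reporting (Safety Assessments; Independent data safety monitoring, item 3).* Reports go to the IRB, the funding agency and, as appropriate, the sponsor. The ward team is not a recipient.
- *Imminent-danger clause (Safety Assessments, after Table 2).* It permits measures "like contacting the primary treatment team and placing the patient on 1:1 observation until evaluation by the primary team". It does not name seizures, and one that has already ended may not count as imminent danger.
- *The PI's position (Study Population, Recruitment).* The PI is an inpatient attending, but the text does not make the PI each subject's treating physician. Item 6 lists the PI's notice to the primary team as a separate step and puts it under the condition.

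None of these orders notice to the ward after a seizure of 5 minutes or less.

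**4. Comparison inside the protocol.** For mania or hypomania, Effects on Mood says "the subject will be withdrawn from the study and the treatment team will be informed in order to initiate adequate treatment", with no duration threshold. The same section provides for sharing worsening suicidal ideation with the treatment team.

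**The case against.** The strongest reply is that care after a short seizure is better than the two lists suggest. Item 2 of the same section has the study physician or nurse monitor the subject during and after rTMS. Item 4 requires one of them to be present, and item 6 has them attend to the subject with standard seizure precautions whatever the duration. Subjects are already under intensive inpatient care with suicide precautions and are seen daily by the treatment team (Effects on Mood). A PI who works on the unit and has just withdrawn a subject mid-course would very probably tell colleagues. The condition may be a drafting slip in which only Ativan was meant to be conditional. All of this stands and narrows the gap. It does not put notice to the ward into the written plan, and a slip is a reason to correct the text.

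The comparison with mania also has limits. Syncope, severe pain and worsening hearing lead to stopping, first aid or withdrawal, with no stated notice to the team. The protocol therefore has no uniform notice standard, and the comparison shows only that it does order notice for some harms.

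A reader might infer more than the documents support, in three ways:

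- *That the patient goes back unwatched and at risk of another seizure.* The monitoring and inpatient care described above count against the first part. On the second, Risks Associated with TMS, item 9, states that seizures caused by rTMS have not resulted in future ones. Stimulation also stops for good once the subject is withdrawn.
- *That an uninformed team may continue bupropion or a tricyclic.* Exclusion Criteria h) vii and viii keep patients on these drugs out at entry. The TMS section also has the PI and a co-investigator adjust the motor threshold if medication changes could affect seizure threshold.
- *That the size of the problem is the chance of a seizure in this trial.* The documents give no rate and list seizure as rare. The point concerns what follows a seizure, and the correction would not change how often one occurs.

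**Conclusion.** The point holds as a defect in the written safety procedure that should be corrected. Two actions that belong after every seizure are tied to a threshold 2.5 times the duration within which the protocol expects most seizures to end. The reason given for the threshold supports only the drug. The consequence is limited: the ward team need not be told of the expected short seizure, while study staff attend, the PI knows, and the subject leaves the study.

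The conclusion rests on reading the condition as covering all three steps beneath it, which is how it is set out. It also rests on there being no other instruction in the document to notify the ward, and none was found. It assumes no seizure rate. It does not establish that patients would in fact be left unobserved, or that a second seizure is likely. No sample size, endpoint or analysis is affected.

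**What to change.** In item 6, leave only the Ativan step under the 5-minute condition. Add the following to the list for every seizure:

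- The PI, study physician or nurse promptly tells the primary clinical team, giving the time, the duration and the stimulation settings.
- The patient returns to the inpatient unit accompanied by staff, by stretcher if needed, and stays under observation until evaluated by the primary team, which then sets the level of observation.

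The end point follows the protocol's own imminent-danger clause, which also runs until the primary team's evaluation. Leaving the later observation level to that team avoids fixing constant observation for every brief event, which nothing in the documents requires.

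In use, the cost is one call and a short period of observation per seizure, in patients who are already inpatients. On paper, the change is a small rewrite of item 6 and a minor amendment that needs IRB approval before it takes effect (Independent data safety monitoring, item 3). What subjects are told about seizure care under item 7 of the same section should be updated to match.

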- 1. Seizures: Seizure induction represents the most serious known risk of TMS (26). Seizures have been reported more frequently in subjects with brain lesions (e.g., stroke) but have rarely been reported in subjects with no history of seizures or neurologic disease. When seizures have been reported, they were almost exclusively in association with a stimulation frequency >1 Hz. Based on an extensive review of the literature, guidelines have been developed that specify the number of stimulations that may safely be given as a function of stimulus intensity (% of Motor Evoked Potential [MEP]) and frequency of stimulation (29). Using these guidelines, there have been few published reports, to our knowledge, of seizures or evidence of after discharge or spread of excitation in normal subjects receiving repetitive TMS who did not have an identified risk factor that is exclusionary for our study (26). We propose to adhere to the published guidelines. Furthermore, as subjects with a history of seizures are more likely to experience seizures due to TMS, these subjects will be excluded.
- 2. Effects on Cognition: A number of studies have been performed to identify possible adverse neuropsychological consequences of TMS. There have been several studies in which a number of cognitive tasks were administered before and after TMS (29, 30). Few adverse effects of TMS on cognition are reported, and there is a trend for performance to be better on measures such as delayed story recall. Two studies, however, have demonstrated possible adverse effects lasting up to one hour. Greenberg et al. (cited in (29)) reported that task switching was impaired after 20-Hz stimulation of the right compared to the left dorsolateral frontal lobe. As there was no untreated condition, this effect may reflect an enhancement of function after the left prefrontal TMS rather than a decrement after right TMS (see Grafman et al. (31)). Flitman et al. (32) reported a significant decrease in logical memory one hour after testing after extensive stimulation using

PI: *[name]* parameters that exceed guidelines for inter-train interval (150 trains of rTMS at 15 Hz, 750 msec duration, and 1.2 times the MEP).

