An unanticipated adverse device effect is defined as "any serious adverse effect on health or safety, or any life-threatening problem, or death caused by, or associated with, a device; if that effect, problem, or death was not previously identified in nature, severity, or degree of incidence in the investigational plan, or application (including supplementary application), or any other unanticipated serious problem associated with a device that relates to the rights, safety, or welfare of subjects." If an unanticipated adverse effect occurs, the investigator will promptly notify the sponsor of such an event within 24 hours of first learning of the event using the FDA Medwatch 3500A form. The form can be found on-line at:

Serious Adverse Events

Each adverse event will be assessed for its seriousness using the criteria outlined below. The term serious adverse event is not synonymous with a "severe" adverse event, which may be used to describe the intensity of an event experienced by the subject. An adverse event will be classified as serious if it meets any of the following criteria:

• Results in, or contributes to, a death

http://www.fda.gov/Safety/MedWatch/HowToReport/DownloadForms/

- Life-threatening (i.e., the subject was, in the opinion of the investigator, at risk of death at the time of the event, but it does not include an event that, had it occurred in a more severe form, might have caused death)
- Results in permanent disability or incapacity (i.e., permanent impairment of a body function or permanent damage to a body structure)
- Requires in-subject hospitalization or prolongs hospitalization
- Necessitates medical or surgical intervention to preclude a permanent disability or incapacity
- Results in a congenital anomaly or birth defect

PI: [name]

Non-serious adverse events are all events that do not meet the criteria for a "serious" adverse event.

If serious adverse event occurs, the investigator will promptly notify the sponsor of such an event within 24 hours of first learning of the event using the FDA Medwatch 3500A form. The can be found on-line at: http://www.fda.gov/Safety/MedWatch/HowToReport/DownloadForms/

The investigator will also promptly notify the IRB of such an event as soon as possible, but no later than ten working days after first learning of the event.

Severity

Each adverse event will be assessed for its severity, or the intensity of an event experienced by the subject, using the following.

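### The seriousness list has no important-medical-event item, so a brief rTMS seizure or a low-lethality suicide attempt on the ward can be classed non-serious and miss the 24-hour sponsor notice

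*Combined protocol and SAP*

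**What the plan says.** The rule in the Serious Adverse Events section is: "An adverse event will be classified as serious if it meets any of the following criteria". Six criteria follow: death, a life-threatening event, permanent disability, hospitalisation or its prolongation ("Requires in-subject hospitalization or prolongs hospitalization"), intervention to avert permanent disability, and congenital anomaly. The section then closes the list: "Non-serious adverse events are all events that do not meet the criteria for a" serious event. Serious events go to the sponsor within 24 hours and to the IRB within ten working days. Unanticipated adverse device effects carry the same 24-hour sponsor clock, and deaths have their own rule of 24 to 48 hours.

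On seizure, item 1 of the rare risks under Risks Associated with TMS opens "Seizure induction represents the most serious known risk of TMS (26" (the quote stops at a citation number). Item 6 of Protection Against Risks Associated with TMS says most seizures end within 2 minutes. It reserves drug treatment for events lasting more than 5 minutes, with this reason: "Knowing that all TMS-induced seizures to date have spontaneously resolved without interventions".

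On suicidality, the Effects on Mood item accepts that rTMS may raise the risk of suicide or suicidal ideation. The last paragraph of Background and Rationale names safety as the primary objective.

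**The concern.** These two events matter most to a safety-first trial of rTMS in suicidal inpatients, and the seriousness rule names neither. The protocol treats a seizure as grave enough for withdrawal and immediate publication, yet nothing guarantees that it is classed serious. Item 12 of the rare risks says the risks listed before it are raised because the planned 5-second trains exceed the 4.2 seconds it attributes to the FDA, so seizure is not a remote possibility in the plan's own terms. A non-fatal suicide attempt is not on the withdrawal list, is not counted by the stopping rule (which counts completed suicides only), and has no reporting rule of its own.

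At stake are the classification of such an event and the time by which the sponsor hears of it. With a target of 20 patients randomised 1:1, a single event would weigh heavily in any statement that rTMS was well tolerated. Its seriousness should not turn on unstructured judgement.

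**Working it through.** No sample size, power or error rate is involved, so the check sets each criterion beside each event. The seizure is the one the protocol describes: short, self-resolving, in an inpatient. The attempt is one of low lethality, made on the ward.

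| Criterion | Brief self-limited seizure | Low-lethality attempt on the ward |
|---|---|---|
| Death | Not met | Not met |
| Life-threatening | Met only if the investigator judges an actual risk of death | Same |
| Permanent disability | Not met | Not met unless lasting injury results |
| Hospitalisation or its prolongation | Met only if the stay is prolonged | Same |
| Intervention to avert permanent disability | Not met if it resolves untreated | Met only if such intervention is needed |
| Congenital anomaly | Not applicable | Not applicable |

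1. Life-threatening. The test is whether "the subject was, in the opinion of the investigator, at risk of death at the time of the event". The text then narrows it: "it does not include an event that, had it occurred in a more severe form, might have caused death". A seizure that would be dangerous only if longer or more violent falls outside.

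2. Disability. "Results in permanent disability or incapacity" does not describe an event that resolves completely.

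3. Hospitalisation. Patients are already admitted during treatment, so the prolongation limb is the one that can operate. The protocol states no expected length of stay against which to judge it.

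4. Result. If the investigator sees no actual risk of death, the stay is not prolonged and no intervention against permanent harm is needed, each event meets none of the six criteria and falls into the non-serious class.

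5. Other routes to a 24-hour notice. The unanticipated-device-effect definition covers effects not already identified in nature, severity or incidence. Seizure and increased suicidality are both listed as risks, so this route is narrowed. It stays open if severity or frequency exceeds what the plan identified. The rule on deaths does not apply.

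6. Routes without a stated clock. Safety Assessments and the Data and Safety Monitoring Plan send any adverse event to the IRB and funding agency, with no deadline. Item 3 of Independent data safety monitoring invokes IRB Policy 10.2 and reporting to the sponsor where appropriate. The policy's content is not in the documents. Item 6 there provides a monitoring board but states no triggers.

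7. What does not depend on seriousness. Data Analysis applies Fisher's exact test to patients with any adverse event. The stopping rule counts completed suicides. Withdrawal after a seizure applies whatever its code.

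**The case against.** The strongest reply is that the gap opens only for an event chosen to meet no criterion. That is fair as far as it goes. A reader might infer that these events will be coded non-serious, or that inpatient status disables the hospitalisation criterion. The documents support neither. Prolongation counts, hospitalisation is one criterion of six, the life-threatening item rests on the investigator's opinion, and the intervention item may apply. A suicide attempt is particularly likely to be caught by one of these, and an attempt after discharge that leads to admission during the 3- and 6-month follow-up meets the hospitalisation criterion directly. A seizure past 5 minutes, with drug treatment, transport and constant observation, might also qualify.

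The second reply is that nothing is hidden. This is also largely right. Adverse events are recorded with MedDRA preferred terms, sessions are videotaped, and a seizure brings PI notification, withdrawal and publication. The sponsor is named as a recipient where appropriate, and Policy 10.2 may set a deadline that cannot be seen here.

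What survives is narrower. The seizure the protocol itself expects is the one most likely to slip through the list, and no sponsor deadline is stated for it when it does.

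**Conclusion.** The point holds as a gap in classification and reporting: these events can be classed non-serious and so lose the explicit 24-hour sponsor notice. The seizure case is stronger than the suicide-attempt case. The conclusion assumes that the stay is not prolonged, that no actual risk of death is judged present and that no intervention against permanent harm is needed. It rests on the protocol's wording alone, without any outside regulatory definition.

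The size is not a number. With roughly 10 to 14 patients on active treatment (20/2 and 28/2), one event would be 1/10 = 10% to 1/14 = 7% of the arm. A reader might infer that a serious-event rate would fall from 7–10% to zero. The documents do not support that as a consequence for a planned result, because Data Analysis specifies no table or rate of serious events. The Fisher test on any adverse event, the stopping rule and the seizure withdrawal rule are all unaffected. This is a worthwhile, inexpensive improvement to safety oversight, and it does not invalidate the planned analysis.

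**What to change.** Add a seventh criterion to the Serious Adverse Events list for important medical events that may jeopardise the patient. State that any seizure or seizure-like reaction and any suicide attempt are always serious, whatever their duration, lethality or effect on length of stay. Apply the existing 24-hour sponsor notice to them, and amend the adverse event form to match. In Data Analysis, state that the safety summary will show these events by arm.

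The change concerns classification and reporting only and leaves clinical management as it is. Adverse events and the C-SSRS are already collected, so no new data are needed. The cost is a short amendment and a few more expedited reports.
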